### Transcriptome Endpoints

The differential gene expression profiles of esophageal biopsies of EoE patients compared to healthy controls is the EoE disease transcriptome ([Sherrill, 2014](#)). This disease gene expression signature was further refined to a smaller gene set to be used as an EoE diagnostic panel (EDP) ([Dellon, 2017a](#)). A gene signature representing type 2 inflammation has been curated from the literature, pre-clinical experiments performed at Regeneron, and dupilumab response signatures from atopic dermatitis and a phase 2 study of EoE (unpublished). The gene lists comprising each one of these transcriptomes can be found in Section 11.6.

Normalized Enrichment Score (NES) reflects the degree to which the activity level of a set of transcripts is overrepresented at the extremes (top or bottom) of the entire ranked list of transcripts within a sample and is normalized by accounting for the number of transcripts in the set ([Subramanian, 2005](#), [Barbie, 2009](#)). NES of the relative change from baseline to week 24 will be calculated for the respective gene sets based on expression levels of each individual gene averaged over 3 esophageal regions (proximal, mid, and distal). If data are missing from region(s), the average will be taken from the available regions for each individual gene.

**EoE Impact Questionnaire (EoE-IQ)**

The EoE-IQ is a disease-specific measure of health-related QoL in EoE patients developed by the sponsor. The EoE-IQ measures EoE impact on emotional, social, work and school, and sleep aspect of a patient. Patient is asked to respond to 11 questions based on experience living with EoE during the past 7 days.

Item No.	Question
■	[REDACTED]
■	[REDACTED]
■	[REDACTED]
■	[REDACTED]
■	[REDACTED]
■	[REDACTED]
■	[REDACTED]
■	[REDACTED]
■	[REDACTED]
■	[REDACTED]
■	[REDACTED]
■	[REDACTED]
■	[REDACTED]
■	[REDACTED]

Response to each item is on a 5-point scale (1 = ‘Not at all’, 2 = ‘A little’, 3 = ‘Somewhat’, 4 = ‘Quite a bit’, 5 = ‘Extremely’). The EoE-IQ average score is the sum of the non-missing responses divided by the number of items with non-missing response (note: response of “I do not go to school or work at a paying job” to item 9 or 10 is considered as missing response). The average score could range from 1 to 5; a higher score is indicative of a more negative impact of EoE on patient QoL.

The EoE Impact Questionnaire will be recorded by the patient using electronic questionnaire at baseline visit (visit 3), week 12, week 24, week 36, week 52 (EOS) or ET visits, and immediately prior to start of rescue medication or procedures.

**EoE Symptom Questionnaire (EoE-SQ)**

The EoE-SQ is a questionnaire measuring the frequency and severity of symptoms other than dysphagia and pain with swallowing. It is developed by the sponsor. The EoE-SQ asks about symptoms that patients with EoE may have (chest pain, stomach pain, burning feeling in your chest, food or liquid coming back up into your throat, throwing up) during the past 7 days. Response to the frequency of each symptom is on a 5-point scale (1 = ‘Never’, 2 = ‘One day’, 3 = ‘2-6 days’, 4 = ‘Once a day’, 5 = ‘More than once a day’). The EoE-SQ frequency score is calculated as the sum of the frequency scores from the 5 items which could range from 5 to 25; a higher score is indicative of higher frequency of symptoms.

Response to the severity of each symptom based on the worst experience in the past 7 days is on a scale of 0 to 10 (higher is worse), with 0 and 10 indicating severity levels for the respective symptoms as follows:

Questions	Severity Scale	
■ [REDACTED]	[REDACTED]	[REDACTED]
■ [REDACTED]	[REDACTED]	[REDACTED]
■ [REDACTED]	[REDACTED]	[REDACTED]
■ [REDACTED]	[REDACTED]	[REDACTED]
■ [REDACTED]	[REDACTED]	[REDACTED]

a Questions 4 and 5 are not included in EoE severity scoring.

The EoE-SQ severity score is calculated as the sum of the severity scores from questions 1 to 3, which could range from 0 to 30; a higher score is indicative of more severe symptoms. If patient answers ‘Not at all’ to an item question about frequency, they will not be asked to answer the corresponding severity question and in that case a severity score of 0 will be assigned for that item.

The EoE Symptom Questionnaire will be recorded by the patient using electronic questionnaire at baseline visit (visit 3), week 12, week 24, week 36, week 52 (EOS) or ET visits, and immediately prior to start of rescue medication or procedures.

Proportion of patients who receive rescue medications or procedures

Rescue medications or procedures are described in Section 0.

**4.4.3. Exploratory Efficacy Variable(s)**

Exploratory efficacy endpoints include:

- Percent change from baseline to week 24 in *average* esophageal intraepithelial eosinophil count (eos/hpf) of 3 esophageal regions
- Percent change in EoE EREFS total score from baseline to week 24
- Absolute change from baseline to week 24 in EREFS (excluding stricture)
- Absolute change from baseline to week 24 in EREFS inflammation subscore
- Absolute change from baseline to week 24 in EREFS remodeling subscore
- Absolute change in EoEHSS total grade score (excluding lamina propria) from baseline to week 24
- Absolute change in EoEHSS total stage score (excluding lamina propria) from baseline to week 24

- Patient global impression of change (PGIC) of dysphagia: proportion of patients who rate their dysphagia symptoms as “a little better”, “moderately better”, or “very much better” at week 24
- Patient global impression of severity (PGIS) of dysphagia: proportion of patients with no symptom and proportion of patients with no symptom or mild symptoms at week 24
- Absolute change in TNSS from baseline to week 24
- Absolute change in POEM from baseline to week 24
- Absolute change in ACQ-5 from baseline to week 24
- Absolute change in RQLQ 12+ from baseline to week 24
- Absolute change in pain related to dysphagia (based on question 4 of the DSQ) from baseline to week 24
- All the above exploratory endpoints assessed at week 24 will be assessed at week 52 as additional exploratory endpoints.

The following DSQ variables (prorated and un-prorated) will be analyzed:

- Absolute change in the prorated 7-day average DSQ score from baseline to week 24
- Absolute change in the un-prorated 7-day average DSQ score from baseline to week 24
- Absolute change in the un-prorated 14-day average DSQ score from baseline to week 24

More details including calculations of DSQ variables are provided below, “[Prorated/un-prorated DSQ score](#)”.

Average esophageal intraepithelial eosinophil count (eos/hpf) of 3 esophageal regions

The average esophageal intraepithelial eosinophil count at each visit is the average of the quantities of eosinophils in the most inflamed HPFs across the 3 esophageal regions. For example, if for a particular patient, at week 24, the quantity of eosinophils in the most inflamed HPF is 2/hpf, 3/hpf, and 4 /hpf from the proximal, mid, and distal regions, respectively, the average eosinophil count is 3/hpf (mean of 2, 3, 4/hpf) for week 24.

EREFS (excluding stricture), Inflammation, and Remodeling Sub-scores

The EREFS (excluding stricture), inflammation, and remodeling sub-scores for each region is the sum of assigned scores for each of the included major features as listed below. The sub-scores summed for the proximal and distal regions will be used for analysis.

Sub-score	Major features included	Range (per region)	Range (proximal+distal)
EREFS (excluding stricture) total score	Edema + Rings + Exudates + Furrows	0-8	0-16
Inflammation subscore	Edema + Exudates + Furrows	0-5	0-10

Remodeling subscore	Rings + Stricture	0-4	0-8
---------------------	-------------------	-----	-----

Patient Global Impression of Severity (PGIS) of Dysphagia

The PGIS is a one-item questionnaire that asks patients to provide the overall self-assessment of difficulty of swallowing food on a 4-point scale for the past week. Response choices are: 1 = ‘none’, 2 = ‘Mild’, 3 = ‘Moderate’, 4 = ‘Severe’. The PGIS will be completed by patients using electronic questionnaire at baseline visit (visit 3), week 12, week 20, week 24, week 36, week 52 (EOS) or ET visits, and immediately prior to start of rescue medication or procedures.

Patient Global Impression of Change (PGIC) of Dysphagia

The PGIC is a one-item questionnaire that asks patients to provide the overall self-assessment of change in difficulty of swallowing food on a 7-point scale, compared to just before patient started taking the study injection. Response choices are: 0 = ‘Very much better’, 1 = ‘Moderately better’, 2 = ‘A little better’, 3 = ‘No change’, 4 = ‘A little worse’, 5 = ‘Moderately worse’, 6 = ‘Very much worse’.

The PGIC will be completed by patients using electronic questionnaire at week 12, week 20, week 24, week 36, week 52 (EOS) or ET visits, and immediately prior to start of rescue medication or procedures.

Total Nasal Symptom Score (TNSS)

The Total Nasal Symptom Score (TNSS) is a 3-item composite symptom assessment of congestion, itching/sneezing, and rhinorrhea for the last week. Each symptom is graded on a 0-3 scale as below:

Score	Symptoms
0	No symptoms
1 = mild	Awareness but not troubled
2 = moderate	Troublesome but not interfering with normal daily activities or sleep
3 = severe	Interfering with normal daily activities or sleep

The TNSS total score is the sum of scores for each of the symptoms (congestion, itching/sneezing, rhinorrhea) and could range from 0 to 9 (a higher score suggests worse nasal symptoms).

The TNSS will be administered only to patients with a documented history of allergic rhinitis and who fluently speak a language in which the questionnaire is presented (based on availability of translations in participating countries). It will be completed by patients at the baseline visit (visit 3), week 12, week 24, week 36, and week 52 (EOS) or ET visits, and immediately prior to start of rescue medication or procedures.

Patient-Oriented Eczema Measure (POEM)

The POEM is a 7-item, validated questionnaire used in clinical practice and clinical trials to assess disease symptoms in children and adults with AD (Charman, 2004). The format is a response to 7 items (dryness, itching, flaking, cracking, sleep loss, bleeding, and weeping) using a 5-point scale, based on frequency of occurrence during the past week. The possible scores for each question were: 0 (no days), 1 (1 to 2 days), 2 (3 to 4 days), 3 (5 to 6 days), and 4 (every day). The total score is the sum of scores for each of the 7 items; a higher score is indicative of more severe AD.

The following POEM banding scores have been established (Charman, 2004): 0 to 2=clear or almost clear; 3 to 7=mild eczema; 8 to 16=moderate eczema; 17 to 24=severe eczema; and 25 to 28=very severe eczema.

If one question of the seven is left unanswered, then that question is scored as 0 and the scores are summed and expressed as usual out of a maximum of 28. If two or more questions are left unanswered, then the questionnaire is not scored and is set to missing.

The POEM will be administered only to patients with a documented history of AD and who fluently speak a language in which the questionnaire is presented (based on availability of validated translations in participating countries). It will be completed by patients at the baseline visit (visit 3), week 12, week 24, week 36, and week 52 (EOS) or ET visits, and immediately prior to start of rescue medication or procedures.

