## 4. ANALYSIS VARIABLES

### 4.1. Demographic and Baseline Characteristics

The following demographic and Baseline characteristics variables will be summarized:

- Demographic variables: Age at screening as a continuous variable and with grouping (years; 12 to <18, ≥18 to <40, ≥40 to <65, ≥65), Sex (Male, Female), Ethnicity with grouping (Hispanic or Latino, Not-Hispanic or Latino), Race with grouping (White, Black or African American, Asian, Other), Region (North America, or Rest of World), Country, Baseline weight as a continuous variable and with grouping (kg; <60, ≥60), Height (m), and calculated BMI (kg/m^2; <15, ≥15-<25, ≥25-<30, ≥30), age [years; 12 to <18, ≥18] and use of PPI at randomization [Yes, No].
- Baseline characteristics:
  - DSQ total score
  - Number of days with dysphagia in the 2 weeks prior to baseline as a continuous variable and with group (4, 5, 6, 7, 8, etc.)
  - Amount of pain patient had experienced when swallowing food from DSQ
  - Peak esophageal intraepithelial eosinophil count (eos/hpf) of three regions (proximal, mid, and distal)
  - Eosinophilic Esophagitis-Endoscopic Reference Score (EREFS) total score
  - Mean stage score from the EoE Histology Scoring System (EoEHSS) summed over 3 regions
  - Mean grade score from the EoEHSS summed over 3 regions
  - Total EoEHSS histology stage score (excluding lamina propria fibrosis) summed over 3 regions
  - Total EoEHSS histology grade score (excluding lamina propria fibrosis) summed over 3 regions
  - Patient global impression of severity (PGIS) level (none, mild, moderate, or severe)
  - EoE Impact Questionnaire (EoE-IQ) score
  - EoE Symptom Questionnaire (EoE-SQ) frequency score and severity score
  - Total Nasal Symptom Score (TNSS) for patients with history of allergic rhinitis
  - Rhinoconjunctivitis Quality of Life Questionnaire score for patients aged 12+ years [RQLQ(S)+12] for patients with history of allergic rhinitis
  - Asthma Control Questionnaire-5 (ACQ-5) score for patients with history of asthma
  - Patient-Oriented Eczema Measure (POEM) score for patients with history of atopic dermatitis
  - European quality of life 5-dimensional scale (EQ-5D) utility index score

- European quality visual analogue scale (EQ VAS)
- Baseline blood eosinophil count as a continuous variable and with grouping (Giga/L; <0.15, ≥0.15; <0.30, ≥0.30; <0.50, ≥0.50)
- Baseline serum total immunoglobulin E (IgE) as a continuous variable and with grouping (IU/mL; <100, ≥100)

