### 5.6.1. Analysis of Co-Primary Efficacy Variable(s)

#### Histologic response (binary endpoint)

The proportion of patients achieving a histologic response of peak esophageal intraepithelial eosinophil (eos) count (from all 3 regions) of  $\leq 6$  eos/hpf at week 24 will be analyzed using the Cochran-Mantel-Haenszel (CMH) test to assess the difference in the proportion of responders in the FAS adjusting for the randomization stratification factors (age group [ $\geq 18$  vs.  $\geq 12$  to  $< 18$  years of age] and use of PPI at randomization [yes vs. no]). Estimates of treatment difference and its 95% confidence interval will be presented.

Data may be collected after the patient discontinued treatment and will be included in the analyses.

To account for use of rescue treatment (see Section 0), patients will be considered as non-responder for all time points subsequent to the use of rescue treatment in the primary analysis.

If week 24 biopsy is performed after the date when the first dose of Part C study drug is administered, patients will be considered as non-responder in the analysis.

Due to COVID-19 restrictions, patients may postpone the week 24 visit until an in-clinic visit can be done for biopsy. Before the biopsy procedure could be performed, study drug would be shipped to patients directly to enable them to extend their current assigned dose regimen of study drug. The data from those delayed week 24 visits will be used in the primary analysis as long as the patients keep the extended dosing before biopsy. However, for patients in whom extended dosing due to COVID-19 is interrupted (i.e. 2 or more consecutive doses or 5 or more doses in total missing during extended dosing period), their week 24 biopsy data will be set to missing and then imputed using MI.

Missing data at week 24 will be handled according to the reason for missingness as follows:

- If the peak esophageal intraepithelial eosinophil count at week 24 is missing due to COVID-19 pandemic, the data will be imputed by multiple imputation (MI) using a random seed number of 6681774 for 10 times based on patients who have non-missing eosinophil counts at week 24. The MI will utilize the regression method with treatment group, randomization stratification, baseline eosinophil count, and week 24 eosinophil count included in the regression model. The imputed week 24 eosinophil counts will

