#### **5.6.2. Analysis of Secondary Efficacy Variables**

##### Binary endpoints at week 24:

Secondary efficacy endpoints that measure binary responses at week 24 will be analyzed in the same fashion as the co-primary endpoint of histologic response of peak esophageal intraepithelial eosinophil count of  $\leq 6$  eos/hpf, including the method to handle missing data .

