#### 5.6.5. Analysis of Exploratory Efficacy Variables

The analysis of other efficacy variables will be the same as the primary analysis described in Section 5.6.1 Section 5.6.2.

The prorated and un-prorated DSQ scores will be analyzed using the same method as the co-primary endpoint of absolute change from baseline in DSQ. Descriptive statistics and the CDF plots will also be provided for adults and adolescents separately.

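### The exploratory PGIS responder endpoints ignore the baseline PGIS collected at visit 3, which costs some precision and makes the responder rate harder to read

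*SAP*

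**What the plan says.** SAP 4.4.3 lists two PGIS endpoints: "proportion of patients with no symptom and proportion of patients with no symptom or mild symptoms at week 24". Neither refers to baseline or requires improvement. PGIS is an "overall self-assessment of difficulty of swallowing food on a 4-point scale for the past week", with levels none, mild, moderate and severe. It is measured before treatment: "The PGIS will be completed by patients using electronic questionnaire at baseline visit (visit 3), week 12, week 20, week 24" and later visits.

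For the method, SAP 5.6.5 says "The analysis of other efficacy variables will be the same as the primary analysis described in Section 5.6.1 Section 5.6.2". Section 5.6.2 adds that "Secondary efficacy endpoints that measure binary responses at week 24 will be analyzed in the same fashion as the co-primary endpoint of histologic response", and 5.6.1 specifies a CMH test "to assess the difference in the proportion of responders in the FAS adjusting for the randomization stratification factors", namely age group and PPI use. CMH is not named for PGIS, but these sections offer no other test for a binary endpoint.

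Baseline PGIS appears in SAP 4.1 as a characteristic to be summarised. It is not a stratum, a covariate or a subgroup (SAP 3.5). Continuous endpoints, by contrast, go to an ANCOVA that includes their own baseline value (5.6.1, 5.6.2).

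**The concern.** The CMH was written for histologic response. There, entry requires a peak count of at least 15 eos/hpf, so nobody meets the threshold of 6 or fewer at baseline. PGIS has no such guarantee: the symptom criteria in Protocol 6.2.1 use diary episodes and the DSQ score, not PGIS.

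Two things follow if a fair share of patients enter as none or mild. Their week-24 status is probably well predicted by baseline, so leaving baseline out wastes precision and lets a chance imbalance move the estimate. The reported rate also mixes patients who improved with patients who were never moderate or severe. A reader using PGIS to support the DSQ result cannot separate the two.

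**Working it through.** **Can a none or mild patient enter?** Protocol 6.2.1 requires at least 4 dysphagia episodes in 2 weeks, at least 2 of them needing a relief measure, and a baseline DSQ of at least 10. Under the SAP 4.4.1 scoring, with all 14 diary days scored:

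- four dysphagia days: 4 × 2 = 8
- two of them relieved by drinking: 2 × 1 = 2
- DSQ = (8 + 2) × 14/14 = 10, which qualifies on a 0-84 scale.

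PGIS looks back one week and entry looks back two, so those four days could all precede the PGIS recall period. A mild rating is plausible; none is possible but should be uncommon.

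**Who counts without changing?** For none-or-mild, anyone rated none or mild at baseline. For no symptom, only those rated none; a mild patient must improve.

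**Effect on the reported rate.** The plan gives no PGIS power or rates, so there is no figure to reproduce. Let q be the share none/mild at baseline, r the week-24 none-or-mild rate in that group, and p the rate in the moderate/severe group. The share of an arm's responders who were already none/mild is qr / [qr + (1−q)p]. As an illustration, assume q = 0.20, r = 0.85 placebo and 0.92 dupilumab, p = 0.30 and 0.55:

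- placebo: 0.170 / (0.170 + 0.240) = 0.41
- dupilumab: 0.184 / (0.184 + 0.440) = 0.29
- risk difference: 0.624 − 0.410 = 0.214, against 0.25 among moderate/severe patients.

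**Effect on power.** I simulated the none-or-mild endpoint with 70 per arm (SAP 2.3), a two-sided 5% test and 20,000 trials per scenario. CMH over age × PPI was compared with CMH over age × PPI × baseline PGIS (none/mild vs moderate/severe). Assumed: 15% adolescents, 70% PPI use, and these week-24 rates (placebo/dupilumab):

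- A: 30%/55% if moderate/severe, 85%/92% if none/mild
- B: 30%/55% and 70%/85% (weakest association)
- C: 35%/60% and 85%/95%

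Dropout is the plan's 15% (SAP 2.3), scored as non-response by multiplying every rate by 0.85. This follows 5.6.1, where a missing value unrelated to COVID-19 is a non-response. Gains in power points from adding baseline PGIS:

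| None/mild at baseline | A, no dropout | A, 15% | B, no dropout | B, 15% | C, no dropout | C, 15% |
|---|---|---|---|---|---|---|
| 5% | 1.3 | 1.4 | 0.4 | 0.6 | 1.0 | 1.2 |
| 10% | 2.9 | 2.6 | 1.3 | 1.2 | 2.0 | 2.0 |
| 20% | 5.8 | 4.2 | 3.0 | 2.3 | 4.7 | 3.9 |
| 30% | 8.2 | 5.0 | 3.8 | 2.7 | 7.3 | 4.0 |
| 40% | 9.5 | 5.3 | 4.5 | 2.9 | 8.3 | 4.6 |

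At 20% under C, for example, power rises from 74.5% to 79.2% without dropout and from 59.3% to 63.2% with it. If nobody is none or mild at baseline, nothing changes. The no-symptom endpoint was not simulated.

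**The case against.** No decision rests on PGIS. It is exploratory, absent from the hierarchy in SAP 5.6.3, and no power is claimed for it. Randomisation balances baseline PGIS in expectation, and an imbalance would show in the baseline table. PGIS is treated like every other binary endpoint. The gain depends entirely on a distribution that the documents do not give, and the entry rules make a baseline rating of none unlikely. All of this stands, and it limits the point to a refinement.

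The obvious remedy, baseline PGIS as a further CMH stratum, also has a real weakness. It gives 2 × 2 × 2 = 8 cells. At the 10% adolescent minimum, about 7 adolescents per arm would be spread over four of them. Patients with no baseline PGIS would drop out unless a rule were written: SAP 5 leaves missing baselines unimputed by default, and 5.6.2 makes an exception only for EoE-IQ and EoE-SQ. A regression model with a missing category answers both.

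A reader might infer that the planned comparison is biased or inflates type I error. It does neither: a CMH that omits a prognostic baseline variable is still a valid randomised comparison. Nor is PGIS the only patient-rated check on the DSQ. PGIC sits beside it, is anchored to just before the first injection and concerns the same symptom, though it asks about recalled change rather than current severity.

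**Conclusion.** The point holds as a minor loss of precision and a harder-to-read responder rate. It applies fully to the none-or-mild endpoint; for the no-symptom endpoint, only patients rated none at baseline count unchanged.

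Under the assumed rates, the loss is about 1 to 3 power points when 5-10% enter as none or mild. At 20-40% it is about 3 to 5 points with 15% dropout scored as non-response, and about 4 to 9 points without dropout. The weakest association sits at or just below the lower end of each range. All of this rests on assumed response rates, baseline shares, adolescent share and PPI use, so it is an illustration and not an estimate for this trial. A claim that the loss must exceed some fixed number of points cannot be supported from the documents. The co-primary analyses are not affected.

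**What to change.** In SAP 5.6.5, state that the PGIS responder endpoints are analysed by a logistic model with treatment, age group, PPI use and baseline PGIS (none/mild vs moderate/severe), reported as a standardised risk difference with 95% CI. Keep the rescue and missing-data rules already planned, and add a missing-baseline category so that the whole FAS is retained. Also report the responder rate by arm among patients moderate or severe at baseline; this answers the readability problem directly.

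The cost is a few lines of SAP text and a slightly more complex model, using a variable already collected. Alpha, the co-primary analyses and trial conduct are untouched. The gain may be negligible if few patients are none or mild at baseline. The power figures above come from a stratified CMH; the logistic model should give a similar gain but was not itself simulated.
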